Procedure Title: SAFE-T Study Protocol

Doc Number: 104-08553

Revision: B Page: 7 of 29

SYNOPSIS

STUDY TITLE	Cardiac Cath Lab Staff Radiation Exposure During Chronic Total Occlusion PCI: CorPath®GRX vs. Manual
SHORT TITLE	SAFE-T Study
PRINCIPAL INVESTIGATOR	[name] (Acting) University of Washington Seattle, WA
	[name] (Emeritus) WellSpan York Hospital York, PA
STUDY SPONSOR	Corindus, Inc Waltham, MA USA
RATIONALE	The PRECISE pivotal trial showed that operators sitting at the CorPath's shielded cockpit had a median 92.5% reduction in radiation exposure when compared to published results. To date there have been no direct randomized comparisons of patient safety and staff radiation exposure comparing robotic-assisted (CorPath GRX) CTO PCI to conventional manual CTO PCI. This study will be a randomized evaluation comparing patient outcomes and radiation exposure of Cardiac Catheterization Laboratory staff in similarly matched coronary CTO PCI procedures.
REGULATORY STATUS	The CorPath GRX System was granted 510(k) clearance (K160121) on October 27, 2016.
FDA CLEARED INDICATION FOR USE	The CorPath GRX is intended for use in the remote delivery and manipulation of guidewires and rapid exchange catheters, and remote manipulation of guide catheters during percutaneous coronary and vascular procedures.
STUDY OBJECTIVE	The objective of this randomized safety and observational study is to demonstrate CorPath GRX CTO PCI is safe, and that Cardiac Catheterization Laboratory staff have no additional exposure to radiation when compared to conventional manual CTO PCI procedures without added procedure time.
STUDY DESIGN	This is prospective, dual-arm, randomized, multi-center, observational study comparing patient outcomes and staff radiation exposure in CTO PCI procedures through 48 hours post procedure or hospital discharge, whichever occurs first.

Procedure Title: SAFE-T Study Protocol Doc Number: 104-08553

Revision: B Page: 8 of 29

SUBJECT POPULATION	Subjects >18 years of age with symptoms suggestive of ischemic heart disease, with TIMI grade 0 flow and a lesion that is thought to be present for more than 3 months.
Number/Location of Sites	This safety and observational study will be conducted at up to no less than three (3) centers.
STUDY DURATION	All subjects will be followed through 48 hours post CTO PCI procedure or hospital discharge, whichever occurs first.
SAMPLE SIZE	At least 90 CTO PCI procedures (45 CorPath GRX (robotic-assisted) / 45 Manual)
EFFECTIVENESS PERFORMANCE MEASURE	Clinical Success Defined as successful CTO PCI revascularization with achievement of <30% residual diameter stenosis (visual estimate) within the treated segment and restoration of antegrade TIMI grade 3 flow, without inhospital major adverse events (MAE).
SAFETY MEASURE	In-hospital MAE MAE that occurs within 48 hours of the CTO PCI procedure or hospital discharge, whichever occurs first.
OTHER MEASURES	Operator Radiation Exposure Cumulative dose the physician receives as recorded from electronic pocket dosimeter during procedure. Staff Radiation Exposure Cumulative dose the staff receives as recorded from electronic pocket dosimeter during procedure. Patient Radiation Exposure DAP (dose-area-product) and/or (AK) air kerma as recorded during the procedure Overall Procedure Time Defined as the time measured from the placement of the first guide catheter to last guide catheter removal. Manual Time Total amount of time away from the cockpit. Actual Time at Cockpit Defined as the time the physician operator spends in the robotic cockpit from first entering the cockpit to procedure end time (guide catheter removal). Fluoroscopy Time Total fluoroscopy (min.) utilized during the procedure as recorded by an Imaging System. Contrast Fluid Volume Total contrast (mL) used during the procedure.

Procedure Title: SAFE-T Study Protocol

Doc Number: 104-08553

Revision: B Page: 9 of 29

Inclusion Criteria	 For a CTO PCI procedure to qualify for this study, the procedure must meet the following inclusion criteria: Age ≥ 18 years; One (1) CTO lesion, successfully crossed with conventional manual techniques; The Investigator deems the procedure appropriate for robotic-assisted CTO PCI with the CorPath GRX System; Individual monitoring of radiation dose, using the pocket dosimeter, was initiated at start of procedure; The subject has been informed of the nature of the study, agrees to its provisions and has provided written informed consent.
EXCLUSION CRITERIA	If any of the following criteria are met, the procedure cannot be included in this study: 1. Failure/inability/unwillingness to provide informed consent, or 2. Cardiogenic Shock; or 3. Perforation which requires treatment (e.g. covered stent, coil and other embolization techniques, or pericardiocentesis). 4. More than one lesion (CTO or non-CTO) to be treated.
RANDOMIZATION	The randomization scheme will utilize random block sizes of 4 or 6. Once the investigator has determined that the procedure is eligible based on inclusion/exclusion criteria, the procedure will be randomized in a 1:1 fashion to either CorPath GRX robotic-assisted CTO PCI or conventional manual CTO PCI. To randomize the procedure, a member of the study staff will select the next sequential number from the electronic data capture (EDC) system and declare the procedure's assignment. The assignment will be logged in the EDC.
INVESTIGATIONAL DEVICE	N/A: CorPath GRX will be used with accordance to the indication cleared by FDA.

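### Randomisation comes after manual crossing, but dose, fluoroscopy, contrast and time are compared as whole-procedure totals with no split at randomisation

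*Protocol*

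**What the plan says.** All references are to the Protocol synopsis.

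- **Inclusion Criteria.** A qualifying procedure must have "One (1) CTO lesion, successfully crossed with conventional manual techniques". It must also satisfy this condition: "Individual monitoring of radiation dose, using the pocket dosimeter, was initiated at start of procedure".
- **Randomization.** "Once the investigator has determined that the procedure is eligible based on inclusion/exclusion criteria, the procedure will be randomized in a 1:1 fashion". The assignment is then recorded in the EDC.
- **Other Measures.** Staff dose is "Cumulative dose the staff receives as recorded from electronic pocket dosimeter during procedure"; operator dose is defined in the same way. Patient DAP or air kerma is what is recorded over the procedure. Fluoroscopy time is "Total fluoroscopy (min.) utilized during the procedure as recorded by an Imaging System" and contrast volume is "Total contrast (mL) used during the procedure". Overall procedure time is "Defined as the time measured from the placement of the first guide catheter to last guide catheter removal".
- **Study Objective.** The trial is to show that "Cardiac Catheterization Laboratory staff have no additional exposure to radiation when compared to conventional manual CTO PCI procedures without added procedure time".

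Two further measures, manual time and cockpit time, divide time only. Cockpit time exists only in the robotic arm, so it gives no between-arm comparison. No measure in the synopsis starts at randomisation in both arms.

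**The concern.** The sequence is: dosimeter on, manual crossing, eligibility decision, randomisation, then robotic or manual completion. The arms can differ only in the last step, yet each outcome also counts the earlier ones. Crossing is done manually in both arms before assignment, so in expectation it contributes the same amount to each. It does not bias the absolute difference in means, but it has two other effects:

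- It adds between-procedure variance that has nothing to do with the device.
- On a ratio or percentage scale it moves the result towards 1.

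Both weaken the trial's ability to detect an increase in exposure or time, or to rule one out. The radiation question is in the study title and the objective, and there are only 45 procedures per arm.

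Who gains depends on an analysis rule the synopsis does not state. Totals favour a conclusion of no extra exposure if the comparison is relative with a margin not rescaled to the whole procedure, or if a non-significant result is read as no increase. With a fixed absolute margin they cost the sponsor power.

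**Working it through.** **Inputs from the Protocol.** Order of events and measurement windows as above; 45 procedures per arm (Sample Size). The synopsis gives no power, effect size, SD or margin behind the 90 procedures, so there is no stated figure to reproduce.

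**Assumed inputs.** None of these is in the Protocol.

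- *f*, the share of the control-arm mean total accrued before randomisation: 0.3, 0.5 or 0.7, with 0.1 and 0.2 as a check.
- *R*, the true post-randomisation ratio of robotic to manual: 1.5.
- Lognormal doses in each phase, with log-SD 0.8 or CV 0.6 (log-SD 0.555).
- Log-scale correlation between phases: 0, 0.3 or 0.6.

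**1. Dilution of the ratio.** Whole-procedure mean ratio = f + (1 − f)R.

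- f = 0.3: 0.3 + 0.7 × 1.5 = 1.35
- f = 0.5: 0.5 + 0.5 × 1.5 = 1.25
- f = 0.7: 0.7 + 0.3 × 1.5 = 1.15

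The absolute difference is 0.5(1 − f) of the control mean total, whether measured on totals or on increments. In simulation both agreed with this to within 0.005.

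**2. Power to detect R = 1.5.** 6,000 simulated trials per setting, two-sided 5% t-test on log dose, 45 per arm:

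| Setting | Totals: f = 0.3 | f = 0.5 | f = 0.7 | Increment |
|---|---|---|---|---|
| log-SD 0.8, corr. 0 | 55% | 40% | 21% | 65–66% |
| log-SD 0.8, corr. 0.3 | 50% | 35% | 19% | 65–66% |
| log-SD 0.8, corr. 0.6 | 46% | 29% | 15% | 65–66% |
| CV 0.6, corr. 0 | 89% | 74% | 38% | 93% |
| CV 0.6, corr. 0.3 | 83% | 62% | 31% | 93% |
| CV 0.6, corr. 0.6 | 77% | 56% | 26% | 93% |

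The loss across the six settings is about 5–21 points at f = 0.3, 19–37 at f = 0.5 and 45–66 at f = 0.7. At smaller shares it is about 0–6 points (f = 0.1) and 2–13 points (f = 0.2). At log-SD 0.8, using the log pre-randomisation dose as a covariate takes the increment analysis to 65%, 69–70% and 84% at correlations 0, 0.3 and 0.6.

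A normal-approximation calculation on the raw dose scale (CV 0.6, correlation 0) gives the same pattern: 87.3% on the post-randomisation dose, against 83.6%, 68.4% and 31.8% on totals.

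**3. Standard error with no true difference.** With equal CVs, dose-scale correlation r and k = f/(1 − f), the SE on totals relative to the increment is √(k² + 1 + 2rk). At r = 0.3:

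- f = 0.3, k = 0.429: √1.44 = 1.20
- f = 0.5, k = 1: √2.60 = 1.61
- f = 0.7, k = 2.333: √7.84 = 2.80

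The squares, 1.44, 2.60 and 7.84, are the factors by which the number of procedures would have to rise to recover the precision. At r = 0 the SE ratios are 1.09, 1.41 and 2.54.

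**4. Ruling out an increase, with an illustrative absolute margin.** Take the margin as half the mean post-randomisation dose, 0.5(1 − f), and no true difference. The chance that the upper 95% limit lies below it (log-SD 0.8, correlation 0.3) is 60%, 38% and 17% on totals, against 73–74% on the increment and 76% with the covariate. With CV 0.6 and correlation 0.3 it is 90%, 69% and 30%, against 96–97%. Here totals work against the sponsor.

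**5. A relative margin.** If a margin of 1.5 is carried to the whole-procedure scale (1.35, 1.25, 1.15), the false pass rate on totals is 2.8%, 2.8% and 2.1%, in line with 2.3–2.7% on the increment. Totals do not inflate the error rate when the margin is rescaled.

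**The case against.** The case on the other side has four parts.

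- **The total is the right quantity.** Staff carry the dose of the whole procedure, and the objective is worded per procedure. On that reading f + (1 − f)R is simply the correct ratio, not a biased one. This stands: totals should be kept, and the defect is lost precision rather than bias. But the precision of the total also depends on having a reading at randomisation to adjust for.
- **Only the synopsis is available.** Readings at randomisation may be specified in the body of the protocol or the case report form. This stands as a limit on the finding. What can be said is that the synopsis definitions name no post-randomisation window.
- **The analysis plan can deal with it.** It can choose the model, scale and margin. It cannot supply a reading that was not captured, so the measurement has to be settled in the protocol.
- **The size is assumed.** This also stands. At f = 0.1 the loss is negligible to about 6 points. For a halving of dose (R = 0.5) with CV 0.6, correlation 0 and f = 0.3, raw-scale power is 99.3% on totals against 99.9%. At f = 0.5 and 0.7 the same case falls to 87.3% and 36.1%, so the effect cannot be dismissed either.

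These are also listed as other measures, apart from the effectiveness and safety measures. Even so, they are the only ones that address the exposure and time parts of the objective.

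**Conclusion.** The concern holds. By the synopsis's own order of events, every exposure and time measure that can be compared between arms includes a manual phase completed before assignment, and none is split at randomisation. The consequence is lost precision and, on a relative scale, attenuation; the absolute difference is not biased.

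The loss ranges from a few power points when little dose precedes randomisation to 45–66 points when 70% of it does, for a true post-randomisation ratio of 1.5. The timing is certain from the text. The magnitude is not, because the share, variances and correlation are all assumed, and a strongly negative correlation between phases would reduce or remove the added noise. This should be fixed as a cheap gain in precision on the trial's title question; it does not invalidate a result.

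**What to change.** 1. At randomisation, when staff are already in the EDC, log the dosimeter readings for the operator and each monitored staff member, DAP/air kerma, fluoroscopy time, contrast volume and clock time.
2. Define the between-arm comparison as the increment from randomisation to removal of the last guide catheter, with the pre-randomisation value as covariate.
3. Report whole-procedure totals alongside. On the absolute scale, the total adjusted linearly for the pre-randomisation value gives the same arm difference and SE as the adjusted increment, so one reading serves both.
4. State the scale on which absence of extra exposure is judged and, if a margin is used, whether it applies to the increment or to the whole procedure.

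**Cost.** One extra set of readings from equipment already running, a few EDC fields, a wording change and a short pause at randomisation. Procedures already completed can be split only where time-stamped logs exist. If the full protocol already collects these readings, only the definitions need changing.

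### Does the definition of Actual Time at Cockpit count later time at the table twice, once as cockpit time and once as Manual Time?

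*Protocol*

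**What the plan says.** Three durations are defined in the Protocol synopsis under Other Measures.

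- The entry for Overall Procedure Time reads: "Defined as the time measured from the placement of the first guide catheter to last guide catheter removal".
- The entry for Manual Time reads: "Total amount of time away from the cockpit". No start or stop is given.
- The entry for Actual Time at Cockpit reads: "Defined as the time the physician operator spends in the robotic cockpit from first entering the cockpit to procedure end time (guide catheter removal").

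Two other entries bear on these. Inclusion Criteria require "One (1) CTO lesion, successfully crossed with conventional manual techniques", and Randomization follows once eligibility is established, so every robotic case has a manual phase before the operator sits down at the cockpit. The Study Objective refers to staff radiation exposure "when compared to conventional manual CTO PCI procedures without added procedure time". Of the three durations, that aim corresponds to Overall Procedure Time.

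The synopsis does not say how exits from the cockpit and re-entries are logged, nor that cockpit time and Manual Time should add up to Overall Procedure Time.

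**The concern.** The cockpit definition starts at first entry and stops at guide catheter removal, not at the moment the operator leaves the cockpit. A reader who takes those two events as the whole rule would subtract one timestamp from the other. Any later spell at the table lies inside that span and is also time away from the cockpit, so it would be counted in both measures.

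If so, robotic use would be overstated, most of all in cases converted to manual work soon after first entry. Operator dose could not be read sensibly against time behind the cockpit's shielding. Manual Time would not settle the matter either, because it pools the manual crossing that every case undergoes before randomisation with returns to the table afterwards.

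**Working it through.** The plan states no figure for these measures, so there is none to reproduce. The check is arithmetic on the definitions.

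**Symbols.** T is Overall Procedure Time, B is time before first cockpit entry (it includes the manual crossing), and L is time at the table after first entry. The documents give no values for any of them, so all minutes below are assumptions. Manual Time is taken to lie within the procedure, which the text implies but does not state.

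**Two readings.**

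- Elapsed interval: cockpit = T − B; manual = B + L; sum = T + L.
- Time in the cockpit: cockpit = T − B − L; manual = B + L; sum = T.

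**Example 1.** T = 120, crossing until minute 60, cockpit 60–80, table 80–100, cockpit 100–120. So B = 60 and L = 20.

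- Elapsed interval: cockpit 120 − 60 = 60; manual 60 + 20 = 80; sum 140. Cockpit time is overstated by 20/40 = 50%.
- Time in the cockpit: 120 − 60 − 20 = 40; manual 80; sum 120. No overstatement.

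**Example 2.** T = 120, first entry at minute 60, full conversion at minute 65 with no return. So B = 60 and L = 120 − 65 = 55.

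- Elapsed interval: cockpit 120 − 60 = 60; manual 60 + 55 = 115; sum 175.
- Time in the cockpit: 120 − 60 − 55 = 5; manual 115; sum 120.

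**Range over L**, with T = 100 and B = 30:

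| L (min) | Manual | Cockpit, elapsed interval | Sum | Cockpit, time in cockpit | Sum |
|---|---|---|---|---|---|
| 0 | 30 | 70 | 100 | 70 | 100 |
| 10 | 40 | 70 | 110 | 60 | 100 |
| 20 | 50 | 70 | 120 | 50 | 100 |
| 30 | 60 | 70 | 130 | 40 | 100 |

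The excess equals L and vanishes when the operator never leaves the cockpit. It arises only on the elapsed-interval reading.

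**Which reading do the words support?** The object measured is time the operator spends in the cockpit; the two events say when counting may begin and when it must end. An operator at the table is not spending time in the cockpit. The label *Actual* points the same way, and so does the companion measure, which counts time away from the cockpit. The elapsed-interval reading needs the words about spending time in the cockpit to be ignored.

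**What depends on it?** Clinical Success, in-hospital MAE, the dosimeter measures, patient dose, Overall Procedure Time, fluoroscopy time and contrast volume are all defined without cockpit time or Manual Time. On either reading a conversion still lengthens Manual Time, so it does not disappear from the data.

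**The case for a change.** The best case for a change is practical. The word *first* concedes that there may be later entries, yet the stop event is the end of the procedure. A site completing a form from the two named events could well record two timestamps and no exits, and exits that were not logged cannot be reliably reconstructed afterwards. With three or more centres, different quantities could be recorded under one name. The Rationale rests on the operator sitting at a shielded cockpit, and in the text at hand cockpit time is the only direct measure of how long that lasted. Adding a sentence and some time fields for the 45 robotic cases would be cheap.

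Part of this stands. The synopsis has no rule for exits and re-entries, Manual Time has no stated bounds, and a site keeping only two timestamps would overstate cockpit time by L. But that would be a departure from what the definition asks to be measured. Whether the case report form or the analysis plan already provides for exits cannot be seen here, and how separate intervals are summed is the kind of detail usually settled there. The synopsis plans no analysis of dose against cockpit time.

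The point about pooling manual crossing with later returns is a request for a further breakdown. Manual Time is offered as a total duration, not as a count of how often the robot was abandoned, and it does give that total.

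**Conclusion.** The double counting is not in the definition. Followed as worded, cockpit time excludes later spells at the table, and with Manual Time confined to the procedure the two add up to Overall Procedure Time (40 + 80 = 120 minutes in the first example). The 50% overstatement comes from the elapsed-interval reading together with assumed times; the documents give no frequency or length of returns to the table.

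The residue is an unstated recording rule that analysts and sites can fill sensibly: sum the in-cockpit intervals up to guide catheter removal, and treat the rest of the procedure as manual. Saying so, or reporting Manual Time before and after first cockpit entry, would be an optional clarification of two descriptive measures. If a site did keep only two timestamps, the error would be L minutes in the cases where the operator left the cockpit, confined to cockpit time and its sum with Manual Time. No change to the plan is called for.

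### The protocol prints the block sizes, so a small number of assignments can be known in advance by investigators who also judge robotic suitability

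*Protocol*

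**What the plan says.** All the relevant text is in the protocol synopsis.

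- **Randomization, block sizes.** The entry says that the scheme uses "random block sizes of 4 or 6". It gives no probabilities for the two sizes and does not say whether lists are kept by site.
- **Randomization, arms.** The ratio and arms are stated as "the procedure will be randomized in a 1:1 fashion to either CorPath GRX robotic-assisted CTO PCI or conventional manual CTO PCI". The synopsis does not use the term open-label, but the operator cannot be unaware of which arm is being performed.
- **Randomization, order of steps.** The draw follows the eligibility decision: "Once the investigator has determined that the procedure is eligible based on inclusion/exclusion criteria". Then "a member of the study staff will select the next sequential number from the electronic data capture (EDC) system and declare the procedure's assignment".
- **Inclusion Criteria.** One of the five criteria is discretionary: "The Investigator deems the procedure appropriate for robotic-assisted CTO PCI with the CorPath GRX System". Another requires that the occlusion has already been crossed manually, so the investigator has seen how difficult the crossing was before the patient is randomized.

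**The concern.** Selection bias at entry needs two things: some ability to foresee the next assignment, and some freedom over whether the patient enters. The synopsis supplies both. Past assignments are visible, the printed sizes let an observer work out some block endings exactly, and the suitability criterion is a matter of judgement.

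If an investigator tended to call difficult cases unsuitable when robotic was expected next, the arms would differ in difficulty. Procedure time, radiation dose and Clinical Success would then be compared between unlike groups. The study objective depends on those comparisons, and the rationale promises similarly matched procedures.

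**Working it through.** The plan states no figure on this point, so there is none to reproduce. The check asks how much an observer can foresee, and how much of that is due to knowing the sizes.

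**Inputs**
- Block sizes 4 and 6, ratio 1:1 (Randomization). The two sizes are assumed equally likely.
- At least 90 procedures and at least three centres (Sample Size; Number/Location of Sites). With three equal centres that is 90 / 3 = 30 each. A list of 30 per site is an assumption.
- The observer is assumed to know the sizes and every earlier assignment on the list.

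**Step 1: the simplest certain case.** Every block balances, so the running difference between arms returns to zero at each block end. A block of 4 cannot push it beyond 2. A difference of 3 can therefore arise only when a block of 6 opens with three alike, and the next three must then be the other arm. The observer need not know where the block began.
- Arrangements of a block of 6: 20, of which 2 open with three alike.
- Probability per block: 0.5 × 2/20 = 0.05.
- Certain assignments per block: 3 × 0.05 = 0.15.
- Mean block length: (4 + 6)/2 = 5, so the share is 0.15/5 = 3% of assignments.

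**Step 2: a second case.** Suppose the block start is known, as it always is for the first block. If the first four split 3:1 without opening three alike, the block cannot be of size 4, so its last two are fixed. That covers 6 of the 20 arrangements (two arms, three positions for the odd one). The expected number in the first block is 0.5 × 6/20 × 2 = 0.30. Later in the list the block start is often unclear, so this case contributes less.

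**Step 3: all cases together, by simulation.** The observer holds weights w over the possible numbers of robotic (r) and manual (m) assignments left in the current block. The probability that the next is robotic is p = Σ w·r/(r + m), updated by Bayes' rule after each assignment. An assignment is certain when p is 0 or 1. Best-guess accuracy is the mean of max(p, 1 − p). The last column is a rule that ignores block sizes and guesses whichever arm is behind so far. Each row uses 5,000 simulated lists.

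| List | Certain | Certain per list | Lists with at least one | Best guess, sizes known | Arm-behind rule, sizes not used |
|---|---|---|---|---|---|
| 30, blocks 4/6 | 5.7% | 1.7 | 52% | 68.8% | 68.8% |
| 90, blocks 4/6 | 5.5% | 5.0 | 87% | 69.1% | 69.2% |
| 30, fixed 4 | 31% | 9.3 | 100% | 70.0% | 70.0% |
| 30, fixed 6 | 25% | 7.5 | 100% | 68.4% | 68.3% |

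Repeat runs on lists of 30 give 5.6% to 5.7%, so 0.056 × 30 = 1.7 certain assignments per list. By symmetry half are robotic, about 0.85 per list.

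**Step 4: what disclosure adds.** On a list of 30 the guess is right 68.8% of the time with the sizes and 68.8% without them. Disclosure adds essentially nothing to guessing accuracy. What it adds is the certainty.

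**Step 5: one list shared by three sites.** In 20,000 lists of 90, each assignment fell to one of three sites at random and each site saw only its own. The arm-behind rule was right 52% of the time. This is a simple rule, not the best possible guess.

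**The case against.** The strongest reply is that the disclosed sizes cause little of the harm feared. Guessing accuracy is the same without them, because it comes from short balanced blocks, which the proposed wording keeps. Only the certain assignments depend on disclosure. Rejecting hard cases when robotic is next uses only the robotic half, under one per list of 30, and a borderline patient has to arrive at that moment. This stands and sets the size of the point.

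Second, the larger figures need site-level lists, or one site that sees nearly the whole list. The synopsis describes only that "a member of the study staff will select the next sequential number from the electronic data capture (EDC) system", which fits a shared list equally well. This also stands, so both ends of the range are shown.

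Third, the design already has safeguards. Eligibility is placed before the draw, the assignment comes from and is logged in the EDC, and random variation of block size cuts certain assignments from 25–31% to about 6%. This is fair. The remaining gap is that concealing the next number does not stop someone deducing it from known sizes and visible history.

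A reader might also infer that suitability is the last thing judged before the draw. The synopsis does not say so: it places eligibility as a whole before randomization and sets no order among the criteria.

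**Conclusion.** The point holds as a minor one. The protocol discloses block sizes in a trial where operators see past assignments and eligibility includes their own judgement, so a few assignments can be known beforehand. The size is about 5.6% of assignments, or 1.7 in a list of 30. It rests on two assumptions: the two sizes are equally likely, and the site sees every earlier assignment on its list. On a list shared by three sites, simple guessing from a site's own assignments is near chance.

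Two stronger readings are tempting, and neither is supported. The first is that printing the sizes makes 69% of assignments guessable; that accuracy exists without the sizes. The second is that the results will favour the device. Nothing shows that cases would be rejected selectively, and no effect on time, dose or Clinical Success has been estimated. The documents support a route to bias that is cheap to close, and no more.

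**What to change.** Replace the block-size sentence in the Randomization entry with: *permuted blocks of randomly varying size, specified in a restricted randomisation document not available to sites*. This removes the basis for most of the certain predictions, but leaves the 69% on a fully visible list almost unchanged. It helps only for lists whose sizes the sites do not already know.

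As a secondary safeguard, set the EDC to release the assignment only after every eligibility item, including robotic suitability, has been entered and locked. This stops eligibility being changed once the assignment is seen. It does not prevent guessing beforehand.

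Adding a third size while still printing the sizes would be a weaker remedy: with 4, 6 and 8 on a list of 30, certain assignments fall from 5.7% to 2.3%, and best-guess accuracy only from 68.8% to 67.5%.

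The cost is protocol wording and one EDC setting, with no added patients or staff.
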